#### 8.2.1.7. Hemorrhage

Hemorrhage, including major hemorrhages, defined as symptomatic bleeding in a critical area or organ, can occur with cobimetinib. In clinical studies with cobimetinib, events of cerebral hemorrhage, GI tract hemorrhage, reproductive tract hemorrhage, and hematuria have been reported. Caution should be used in patients with additional risk factors for bleeding, such as brain metastases, and in patients that use concomitant medications that increase the risk of bleeding (including antiplatelet or anticoagulant therapy).

#### 8.2.1.8. CPK elevations and rhabdomyolysis

CPK elevations have been observed in patients who received cobimetinib monotherapy, as well as in patients administered cobimetinib in combination with other agents. The majority of CPK elevations reported were asymptomatic, non-serious, and resolved with or without study drug

interruption. One event of rhabdomyolysis was reported in the Phase III Study GO28141 (cobimetinib + vemurafenib), and rhabdomyolysis has been reported in postmarketing experience. In Study GO28141, CPK elevations was reported as an AE more frequently in patients treated with cobimetinib + vemurafenib (32.4% all grades, 11.3% Grade 3 events) than with placebo + vemurafenib (8.1% all grades, 0% Grade 3 events).

#### 8.2.1.9. Potential embryofetal toxicities

The effect of cobimetinib on human fertility is unknown. No dedicated fertility studies in animals have been performed with cobimetinib. In repeat-dose toxicology studies, degenerative changes were observed in reproductive tissues including increased apoptosis/necrosis of corpora lutea and seminal vesicle, epididymal and vaginal epithelial cells in rats, and epididymal epithelial cells in dogs.

There are no data regarding the use of cobimetinib in pregnant women. When administered to pregnant rats, cobimetinib caused embryolethality and fetal malformations of the great vessels and skull at systemic exposures approximately 0.9 to 1.4 times the human clinical plasma AUC exposure. Therefore, teratogenicity and developmental toxicity is a potential risk for cobimetinib, and cobimetinib use is not recommended during pregnancy. The use of effective forms of contraception (as defined in appendix C) during treatment with cobimetinib and for the duration after the last dose as described in the protocol is mandated.

### 8.3. Idasanutlin

## 8.3.1. Anticipated Toxicities

Th	e majority of AEs recorded for idasanbutlin are transient in nature and reversible.
	Diarrhea
	Nausea
	Vomiting
	Anorexia
	Fatigue/ asthenia
	Thrombocytopenia
	Neutropenia and febrile neutropenia
	Anemia
	Pyrexia
	Sepsis
	Pneumonia
	Fungal Infections
	Electrolyte Disorders (most commonly Hypokalemia)

## 8.3.2. Toxicities Considerations

#### 8.3.2.1. **Gastrointestinal Toxicities**

Gastrointestinal toxicity has early onset and occurs frequently within hours from dosing. Prophylactic antidiarrheal has shown efficacy in moderating symptoms. Antidiarrheal prophylaxis is recommended, but not mandatory, for patients who will be treated with idasanutlin. If necessary, an oral loading dose of 4 mg loperamide 30 minutes before the administration of study medication has been successfully used to reduce the frequency and severity of diarrhea. If diarrhea occurs, 2 mg loperamide should be administered orally every 4

□ Tumor Lysis Syndrome

hours or after every unformed stool to a maximum dose of 16 mg per 24 hours. It is recommended to monitor concomitant causes of GI toxicity, including Clostridium difficile infection, malabsorption/lactose intolerance, fecal impaction, dietary supplements high in fiber, and medications (e.g., stool softeners, laxatives, and antacids). Additional dietary measures could help to minimize risk. It is advised to discontinue all lactose-containing products, alcohol, and high osmolar supplements. Patients should be instructed to eat frequent small meals that include food with anti-diarrheal properties such as bananas, rice, apples, and toast. If diarrhea ≥ Grade 2 occurs, electrolytes need to be monitored at least daily and adequate hydration may be achieved if necessary through IV fluids for electrolyte correction.

Treatment to mitigate emesis may be given prophylactically and is strongly encouraged. The risk of nausea/vomiting should be managed symptomatically throughout treatment with idasanutlin. From 30 to 60 minutes before administration of study, 5-HT3-receptor antagonist administration with or without dexamethasone orally or IV may be sufficient to control symptoms. Rescue medication may include blockers of neurokinin 1 receptor (NK-1 RA). It is recommended to administer IV fluids and correct electrolytes as clinically required.

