# 7.5. Definition of Dose-Limiting Toxicity (DLT) – for patients on idasanutlin armonly

Any of the following events that occur during cycle 1 (first 6 weeks) will be considered a DLT when classified as possibly, probably or definitively related to study treatment (according to NCI CTEP Adverse Event Reporting Requirements). Apart from the criteria listed below, if a lower grade AE leads to a dose interruption of more than 14 consecutive days of study drugs for the first 4 weeks of Cycle 1, this AE will be considered a DLT; patients must receive at least 75% of study drug during cycle 1 in order to be evaluable for the DLT observation period. Whenever a patient experiences toxicity that fulfills the criteria for a DLT, treatment with the study drug responsible for the toxicity will be interrupted (patient may continue the remainder study drugs) and the toxicity will be followed up. The Protocol Chair must be notified immediately of any DLT:

TOXICITY	DLT CRITERIA			
	Anemia CTCAE Grade ≥ 3 > 14 consecutive days			
	Febrile neutropenia CTCAE Grade ≥ 3			
5	ANC CTCAE Grade 3 for > 14 consecutive days			
Blood and lymphatic system disorders	ANC CTCAE Grade 4			
system disorders	Platelet count CTCAE Grade 3 for > 7 consecutive days and/or with signs of bleeding			
	Platelet count CTCAE Grade 4			
Ocular diserders	CTCAE Grade ≥ 2 for > 14 days			
Ocular disorders	CTCAE Grade ≥ 3			
General disorders and administration site conditions	Fatigue CTCAE Grade 3 for > 14 consecutive days			
Skin and subcutaneous tissue disorders	Skin, mucosal or nail toxicity CTCAE Grade ≥ 3 for > 14 consecutive days despite treatment			
GI disorders a	Diarrhea CTCAE Grade ≥ 3 for ≥ 48 hrs, despite the use of anti- diarrhea therapy			
Gi disorders*	Nausea/vomiting CTCAE Grade ≥ 3 for ≥ 48 hrs, despite the use of anti-emetic therapy			

TOXICITY	DLT CRITERIA			
	Constipation CTCAE Grade ≥ 3 for ≥ 48 hrs, despite the use of anti-constipation therapy			
	Blood bilirubin c CTCAE Grade 2 for > 7 consecutive days			
	Blood bilirubin c CTCAE Grade ≥ 3			
Investigations b	AST or ALT CTCAE Grade ≥ 3 in conjunction with blood bilirubin c CTCAE Grade ≥ 2 of any duration			
	AST or ALT CTCAE Grade 3 for > 7 consecutive days			
	AST or ALT CTCAE Grade 4			
	Alkaline phosphatase CTCAE Grade 4			
	Any other CTCAE ≥ Grade 3 toxicity except for:			

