Other hematologic and non-hematologic	Decreased lymphocyte count [lymphopenia] that is not clinically significant			
toxicities	Grade 3 fatigue for less than 7 days			
	
 
Grade 3 diarrhea, nausea/ vomiting, or constipation for less or equal to 48 hours with appropriate supportive medication
 
			

a Patients will not initially receive prophylactic treatment for nausea/vomiting during Cycle 1. However, prophylactic treatment may be initiated in all patients at the dose level where these toxicities have been observed and in all further patients if at least 1 patient has experienced nausea/vomiting CTCAE Grade ≥ 3 or if at least 2 patients experienced nausea/vomiting CTCAE Grade ≥ 2. However, anti-emetics may be applied for treatment if the patient has experienced nausea/vomiting CTCAE Grade ≥ 1 at the discretion of the treating physician.

b For any hepatic toxicity CTCAE Grade 4, or CTCAE Grade 3 that does not resolve within 7 days to CTCAE Grade ≤ 1 (or CTCAE Grade ≤ 2 if liver infiltration with tumor present), an abdominal CT scan should be performed to assess if it is related to disease progression.

Apart from the criteria listed above, if a lower grade AE leads to a dose interruption of more than 14 consecutive days of Idasanutlin, this AE may be considered as DLT (the determination will be based on clinical significance and patient risk; discussion with the Protocol Chair will determine if the event should or should not count as a DLT).

Patients whose treatment is interrupted or permanently discontinued due to an AE or clinically significant laboratory value, must be followed as outlined in the table below, at least once a week for 4 weeks, and subsequently at 4-week intervals, until resolution or stabilization of the event, whichever comes first. Patients that require a dose delay of > 28 days due to a cause unrelated to study participation will have the opportunity to continue study if deemed eligible to do so by the Protocol Chair of the study.

<sup>c Refers to total bilirubin.

Hematology	If 2: CTCAE grade 3 neutropenia, anemia or thrombocytopenia have been demonstrated, these parameters must be repeated at least once a week until resolution to s CTCAE grade 1 to allow for initiation of re-treatment.

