# 7.6. Definition of Maximum Tolerated Dose (MTD) – for patients on idasanutlin arm only

The MTD will be defined as the highest dose tested in which a DLT is experienced by 0 out of 3 or 1 out of 6 patients among the dose levels. The first cohort of patients (3 patients) will be started at dose level 1, and each patient will be observed for 6 weeks on the specified dose:

If no patient in the first cohort of 3 experiences a DLT, accrual will continue to test the next dose level
If 1 patient experiences a DLT any given cohort/ dose level, an additional cohort of 3 patients will be treated at the same dose level
If 1 patient has a DLT out of 6 patients treated at this same dose, accrual will continue to test the next dose level
If 2 or more patients in 3 or 6 patients treated at a given dose experience DLT, the dose will be de-escalated to the next lower dose level. If the current dose level is at -1, the regimen will be considered too toxic and the corresponding cohort within the study will be discontinued
If 0 out of 3 or 1 out of 6 patients has a DLT treated at dose level 3, accrual will continue to the phase II portion of the study

No new cohort of patients will be treated until the previous cohort has been fully evaluated for toxicity and a dose escalation decision has been made. Routine updates regarding patient and study status will be conducted.

Once the MTD is reached, the expansion component of the study will be completed to assess tolerability and efficacy. Patients in the phase II portion of the study will initiate study treatment at the MTD defined in the escalation component of the trial. Note that dose reduction within patients (individually) is allowed after the 4 week DLT observation period in the escalation and in the expansion components of the study (see Dose Modification guidelines, Section 8). Intrapatient dose escalation will not be allowed. Dose reduction will be required for a given patient in case of:

- ☐ Grade 3 or 4 toxicities
- Grade ≥ 2 elevation of creatinine, bilirubin, AST, or ALT lasting more than 14 days despite medical treatment, or
- Grade ≥ 2 ocular, skin or nail toxicity for more than 28 days in a row despite optimal medical treatment, or
- Grade ≥ 2 GI toxicity lasting more than 14 days despite medical treatment.

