# 7.7. Concomitant Treatment and Supportive Care Guidelines

There is a potential for interaction of cobimetinib with other concomitantly administered drugs through the cytochrome P450 system, and should not be used with strong inhibitors or inducers of CYP3A4. The case report form must capture the concurrent use of all other drugs, over-thecounter medications, or alternative therapies. Patients taking any of the prohibited medications on the Prohibited Medications list are excluded from entering the study. This list can be found in the supplemental packet. Patients already enrolled in the study that initiate and persist taking any of the medications on the Prohibited Medications list (except for weak inhibitors) will be discontinued from the study. No apparent drug interactions have been identified for idasanutlin, but strong inhibitors and/or inducers of CYP2C8 and CYP3A4/5 may affect idasanutlin exposure. For idasanutlin, CYP2C8 inhibitors should be avoided when CYP3A4 inhibitors are allowed, since the risk of simultaneous administration of CYP3A4 and CYP2C8 inihibitors is unknown.

Patients on chronic medications that can be given concomitantly with Cobimetinib or Idasanutlin should be maintained on the same dose and dose schedule throughout the study period, as medically feasible. Caution should be used in patients on antiplatelet or anticoagulant therapy due to the risk of bleeding with cobimetinib. The investigator should instruct the patient to notify the study site about any new medications he/she takes after the start of the study drug. All medications (other than study drug) and significant non-drug therapies (including physical therapy and blood transfusions) administered after the patient starts treatment with study drug, and any changes in dosing should be recorded.

All supportive measures consistent with optimal patient care can be given throughout the study at the discretion of the treating physician, as long as they are not part of the list of prohibited medications (located in the supplemental packet). In general, the use of any concomitant medication/therapies deemed necessary for the care of the patient is permitted with the following considerations:

- □ Prophylactic anti-emetics should be started only once the patient experienced nausea or vomiting at the discretion of the investigator.

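### Sections 7.5, 7.7 and 8.3.2.1 give three conflicting rules on anti-emetic prophylaxis with idasanutlin, so Phase Ib patients can be assessed for DLT under different conditions; the likely effect on the MTD is small

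*Combined protocol and SAP*

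**What the plan says.** Three places govern anti-emetic prophylaxis for the same idasanutlin patients.

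- **Section 7.5, footnote a to the DLT table:** "Patients will not initially receive prophylactic treatment for nausea/vomiting during Cycle 1". The footnote then relaxes this. After one patient with Grade 3 or worse nausea/vomiting, or two with Grade 2 or worse, "prophylactic treatment may be initiated in all patients at the dose level where these toxicities have been observed", and also in all later patients. Anti-emetics as treatment are allowed from Grade 1.
- **Section 7.7, concomitant treatment:** "Prophylactic anti-emetics should be started only once the patient experienced nausea or vomiting at the discretion of the investigator". The trigger here is the individual patient's own history, not the cohort's.
- **Section 8.3.2.1, idasanutlin gastrointestinal toxicities:** "Treatment to mitigate emesis may be given prophylactically and is strongly encouraged". It describes giving a 5-HT3 antagonist 30 to 60 minutes before dosing. It adds "The risk of nausea/vomiting should be managed symptomatically throughout treatment with idasanutlin" and carves out neither Cycle 1 nor Phase Ib.

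The DLT table in Section 7.5 lists "Nausea/vomiting CTCAE Grade ≥ 3 for ≥ 48 hrs, despite the use of anti-emetic therapy". Section 7.6 acts on the count: "If 2 or more patients in 3 or 6 patients treated at a given dose experience DLT", the dose goes down one level. Section 24.1 uses the same 3+3 logic to set the MTD and RP2D.

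**The concern.** A 3+3 decision rests on three or six patients, so it matters that they are observed under the same supportive-care rule, or under a rule whose changes are planned and recorded. Idasanutlin is taken on Days 1 to 5, and Section 8.3.2.1 notes that gastrointestinal toxicity often starts within hours of a dose. Whether prophylaxis was given is therefore settled at the moment the risk arises. In a multicentre trial, one site may follow the DLT footnote and another the toxicity section, with both believing they comply.

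One extra DLT changes the decision: 0 of 3 becomes 1 of 3 (expand instead of escalate), 1 of 3 becomes 2 of 3 (de-escalate instead of expand), and 1 of 6 becomes 2 of 6 (de-escalate instead of escalate). The RP2D then goes into the Phase II idasanutlin arm.

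**Working it through.** **Step 1: apply the three rules to the same patient.** The plan states no operating characteristic for Phase Ib, so there is no figure to reproduce. The test is whether the rules give the same answer.

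| Situation | 7.5 footnote a | 7.7 | 8.3.2.1 |
|---|---|---|---|
| First patient at a dose level, Cycle 1 Day 1, no earlier events | Not given | Not started | Strongly encouraged |
| Symptom-free patient in Cycle 1, cohort trigger already met by others | May be given | Not started | Strongly encouraged |
| Patient with Grade 1 nausea in Cycle 1, cohort trigger not met | Not given (treatment allowed) | May start | Strongly encouraged |
| Symptom-free patient after Cycle 1 | Silent | Not started | Strongly encouraged |

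Each pair of sections disagrees in at least one row. Section 7.5 and Section 7.7 are separate rules: rows two and three show them pointing in opposite directions. Row four shows that the 7.7 and 8.3.2.1 conflict persists after the DLT window.

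**Step 2: how far could this move the 3+3?** With per-patient DLT probability p, the chance of escalating past a dose level is

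P(escalate) = (1 − p)³ + 3p(1 − p)² × (1 − p)³.

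At p = 0.20: 0.512 + 3 × 0.20 × 0.64 × 0.512 = 0.512 + 0.197 = 0.709.

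Suppose that going without prophylaxis adds an independent nausea/vomiting DLT risk a, so that q = 1 − (1 − p)(1 − a). Both the base of 0.20 and the values of a are assumptions, because the plan gives neither.

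| a | q | P(escalate) | Change from 0.709 |
|---|---|---|---|
| 0.02 | 0.216 | 0.674 | about −3.5 points |
| 0.05 | 0.240 | 0.622 | about −9 points |
| 0.10 | 0.280 | 0.536 | about −17 points |

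**Step 3: which row is nearest to the protocol's own data?** Section 3.7.2.3 reports, for Study NP27872:

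- nausea DLTs in 2 of 99 patients (2%);
- gastrointestinal DLTs of any kind in 3 of 99 (3%);
- blood and lymphatic DLTs in 19 of 99 (19.2%);
- any DLT in 11 of 34 (32%) on the 5-day schedule.

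Taking p = 11/34 = 0.324 gives P(escalate) = 0.447. Removing the whole nausea share, 0.324 − 0.020 = 0.303, gives 0.488, a change of about 4 points. The two fractions have different denominators, so this shows scale only. The top row of the table is therefore the nearest; the bottom row assumes about five times the observed nausea DLT rate.

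**The case against.** The best case on the other side has four parts.

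1. **The DLT criterion sets a common floor.** An event counts only if it is Grade 3 or worse, lasts at least 48 hours, and persists on anti-emetics. The catch-all row of the DLT table exempts Grade 3 nausea or vomiting lasting 48 hours or less with supportive medication, and treatment may begin at Grade 1. This stands, and it is the main reason the effect is probably small. A reader might infer that any Grade 3 episode is a DLT; the table does not say that.
2. **The specific rule could govern the general one.** Footnote a is written for Cycle 1 and sits under the DLT table, while 8.3.2.1 is permissive, so a site following 7.5 breaches nothing in 8.3.2.1. The reverse is not true: a site that acts on the encouragement in 8.3.2.1 departs from footnote a. No text states precedence, and this reading leaves the conflict with 7.7 unresolved.
3. **Mixed conditions are partly intended.** Footnote a's trigger already lets earlier patients be assessed without prophylaxis and later ones with it. This stands. The contradiction cannot be blamed for all of the mixture, and it would be wrong to say that prophylaxis is barred throughout Cycle 1.
4. **Recording is already required.** Section 7.7 has the case report form capture all other drugs, and the study calendar schedules concomitant medication review. This stands, so no new data collection is needed.

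A reader might also infer that the RP2D will be set under one prophylaxis condition and used under another. The documents do not establish this. Footnote a restricts only Cycle 1, so some change afterwards is implied by design, and Section 24.1 lets the RP2D be adjusted for overall tolerability after cycle 1.

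**Conclusion.** The conflict is real and is in the current text: three operative rules, no order of precedence, and the same patients in the DLT window. It follows that DLTs can be counted under different prophylaxis conditions depending on the section a site reads. It does not follow that they will be, or that the MTD is unreliable.

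The likely effect on escalation is a few percentage points if the earlier 2 of 99 is a fair guide. That figure has limits: it comes from idasanutlin without atezolizumab, and the protocol does not say what prophylaxis those patients received, so the risk without prophylaxis could be higher. The larger shifts in the table rest on assumed added risks of 5 and 10 points, which nothing in the documents supports.

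The direct effect is confined to Phase Ib and so to the MTD and RP2D. The Simon boundaries and error rates in Section 24.3.1 do not depend on DLT counts. This is an internal inconsistency worth correcting, not a flaw in the efficacy design.

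**What to change.** Amend Section 7.5 footnote a, Section 7.7 and Section 8.3.2.1 so that they state one consistent rule for the DLT window. The amended text should say:

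- whether footnote a's cohort trigger stands, and how it relates to the patient-level trigger in 7.7;
- whether the encouragement in 8.3.2.1 applies within the DLT window or only outside it;
- whether the same rule carries into Phase II.

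A consistent rule need not mean one unchanging condition for every patient: a toxicity-triggered switch is compatible with it if all three sections describe the same switch. Which rule applies is for the sponsor's clinical team.

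In the DLT listing used for each escalation decision, show every patient's prophylaxis status at the time of assessment, taken from the concomitant medication data already collected. The cost is amendment wording and one column in a listing; sample size and analysis do not change.

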#### 8.3.2.2. Hematological Toxicities

Patients treated with idasanutlin are at increased risk for infections for the effect on bone marrow progenitors and the related cytopenia. Patients should be closely monitored for infection, and prompt therapy and diagnostic procedures need to be performed as necessary. Idasanutlin has exposure-dependent suppressive effects on bone marrow progenitors. Prophylactic platelet transfusion is recommended when platelet count is < 10 x109/L or local institutional guidelines, and therapeutic transfusions are recommended when clinically indicated (any platelet value in the presence of hemorrhagic symptoms). The hemoglobin level should be maintained at > 9 g/dL in patients with documented cardiac insufficiency (ejection fraction < 50%). Growth factor support may be given per local guidelines for hematologic or solid tumor malignancies.

## 8.4. Atezolizumab

## 8.4.1. Anticipated Toxicities

The PD-L1/PD-1 pathway is involved in peripheral tolerance; therefore, such therapy may increase the risk of immune-mediated adverse events, specifically the induction or enhancement of autoimmune conditions. Adverse events with potentially immune-mediated causes include:

Fatigue
Arthralgia
Asthenia
Anorexia
Diarrhea
Dyspnea
Urinary Tract Infection
Cough
Pruritis
Nausea
Fever
Rash
Vomiting
Musculoskeletal pain
Chills

Protocol Version 3/14/2019

BRE 17107: Atezolizumab, Idasanutlin and Cobimetinib in metastatic ER+ breast cancer VANDERBILT VANDERBILT Protocol Chair: [name]

Dysphagia
Hypotension
Nasal congestion
Нурохіа
Flu-like symptoms
Thrombocytopenia
Abdominal pain
Diabetes
Nephritis
Endocrinopathies including hypothyroidism, hyperthyroidism, hypophysitis, adrenal insufficiency
Hepatitis/transaminitis
Pneumonitis
Colitis
Neurological disorders such as Myasthenia gravis, Guillian-Barre syndrome, and meningoencephalitis
Infusion-related reactions
Myocarditis
Pancreatitis

